9.1.4. Posttreatment Phase (Follow-up)

Days 7 to 28

Subjects will be evaluated for a total of 28 days after randomization. If they are not hospitalized they will be required to return to the hospital for follow-up assessments as an outpatient on Day 7, Day 10, Day 14, and Day 28 as indicated in the [Time and Events Schedules](#). On Day 28 all subjects will complete the study either as an inpatient or outpatient.

Should the study drug duration be increased to up to 10 days (following review of the data by the IDMC, refer to Section [11.10](#), Independent Data Monitoring Committee), additional study drug may be provided if needed. If a subject is discontinued from study drug, a follow-up visit will be scheduled 2 days (+2 days), 5 days (+2 days), 9 days (+2 days), and 23 days (±2 days) after the last dose of study drug was administered. Assessments should be performed as indicated in the [Time and Events Schedules](#), respectively for the Day 7, Day 10, Day 14, and Day 28 visits.

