10.1. Did the child only vomit when coughing [*recall period*]? (select one)

- No
- Yes

11. Did the child eat, drink or nurse as usual [*recall period*]? (select one)

- Yes, ate, drank or nursed as usual
- No, a little less than usual
- No, a lot less than usual
- No, did not eat, drink or nurse at all

12. Was the child receiving liquids other than medicine through tubes in the nose, mouth or stomach [*recall period*]? (select one)

- Yes
- No

13. Did the child urinate as usual (number of wet diapers or trips to the toilet) [*recall period*]? (select one)

- Yes, as usual
- No, a little less than usual
- No, a lot less than usual
- No, did not wet a diaper or use the toilet

14. Did the child show any of these signs [*recall period*]? (note all that apply)

- Dry skin or lips
- Soft spot on top of the head sunk in
- Sunken eyes
- Dark yellow urine
- Little or no urine
- None of these [*cannot be checked if other options are selected*]

15. Did the child's heart seem to be beating faster than usual?

- Yes
- No

Questions 16-17 are to be completed on the day of hospital discharge and during the morning assessment only through follow-up Day 14

16. Please take and record the child's temperature now

Temperature: ° Fahrenheit (*or Celsius as used locally*)

17. [15 second countdown timer]. Please count how many times the child breathes. Press the button to start the timer. When you hear the first tone, begin counting the child's breaths. **Each time the child breathes in and out counts as 1 breath.** When you hear the second tone, stop counting and record how many breaths you counted.

Start Timer [note: 5 second delay after activating the timer before tone indicating begin timing]

Do you need to count again?

- Yes [back to Start Timer]
 No [go to Enter Count]

How many breaths did you count? [] breaths

At every assessment

18. How many hours did you spend with the child [recall period]?
[] hours
19. How many hours were you unable to do things you usually do such as go to work, household chores, or care for other family members because the child had RSV [recall period]?
I missed [] hours from my usual activities because of the child's RSV

For clinical trials only during AM assessment on Day 7 only

20. In general, how did the child react when he/she was given the medicine? (note all that apply)
- Child took medicine easily [cannot be checked if other options selected]
 - Disgusted expressions after tasting medicine
 - Cried after tasting medicine

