5.3. Secondary Endpoints

5.3.1. Definitions

Formulae to be used for derived variables, including data conversions, are provided in the tables below. Note that for time-to event variables the actual date times will be used.

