Viral load status at each time point (categorical)	
Each RSV viral load measurement will be assigned to one of the 3 categories below:
 
 Undetectable (<LOD) Detectable (<LOQ) Quantifiable (\geq LOQ)
Viral load status at each time point (binary)	
Each RSV viral load measurement will be assigned to one of the 2 categories to identify if it is undetectable. Categories will be Yes (1) or No (0).

Time to virus undetectable (hours) [Time-to event]	
The time in hours from initiation of study treatment until the first post baseline time point at which the virus is undetectable in an assessment and after which time no detectable virus assessment follows (= event).
 
For each subject in the ITT-i it will be assumed that the subject is detectable or quantifiable at baseline (even if the value is negative).
 
Subjects will be (right-) censored at the last time observation of a detectable viral load. Subjects for which this last assessment is the baseline assessment will be censored at time 0.
 
(Date and time of event or censoring - date and time of first dose of study drug)/3600, rounded to one decimal.

Time to virus undetectable (hours) [interval censored]	
The time in hours from initiation of study treatment until the first post baseline time point at which the virus is undetectable, using interval censoring.
 
The boundaries of the censoring intervals are defined as the number of hours from the start of treatment.
 
The left boundary of the interval is the last positive assessment before the first confirmed negative sample which is not followed by a confirmed positive sample (at baseline every subject is considered positive). If no negative samples are observed, the left boundary will be the last sample obtained.
 
The right boundary of the interval is the first confirmed negative sample which is not followed by a confirmed positive sample. If this is not observed, the interval is right censored.
 
A confirmed positive sample is defined as two consecutive non-negative samples; a confirmed negative sample is defined as two consecutive negative samples.
 
Last obtained sample, whether positive or negative, is always

	considered confirmed.
--	-----------------------

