Time to end of noninvasive mechanical ventilation support (hours) [Time-to event]	
The time from first dose of study drug to the last end date and time of noninvasive mechanical ventilation and invasive mechanical ventilation support (= event) in hours. Noninvasive mechanical ventilation and invasive mechanical

Measurement	Formula
	
ventilation are defined as indicated on the Oxygen Supplementation form: Type of supplemental oxygen administration.
 
Derivation similar as “Time to end of Oxygen supplementation”

Time to end of invasive mechanical ventilation support (hours) [Time-to event]
	
The time from first dose of study drug to the last end date and time of invasive mechanical ventilation support (= event) in hours. Invasive mechanical ventilation support is defined as indicated on the Oxygen Supplementation form: Type of supplemental oxygen administration.
 
Derivation similar as “Time to end of Oxygen supplementation”

Time to end of supplemental feeding/hydration (hours) [Time-to event]
	
The time from first dose of study drug to the last end date and time of supplemental feeding/hydration (e.g. IV catheter/nasogastric tube) (= event) in hours.
 
Derivation similar as “Time to end of Oxygen supplementation”

Time to return to pre-RSV disease level for respiratory rate (hours) [Time-to event]
	
The time from first dose of study drug until the time to return to pre-RSV disease level. The return to pre-RSV disease level occurs when the observed value of the parameter is indicated by the investigator as normal, and no later observed values are indicated by the investigator as abnormal (=event).
 
Normalization of respiratory rate (RR) will be derived from the answer to the corresponding question in the questionnaire “is this Respiratory Rate value normal for this patient?”
 
If no deterioration from pre-RSV disease levels occurred, the time will be set to time of first dose of study drug and the value will be set to 0 hours.
 
Subjects with an abnormal value at the last assessment will be censored at that time. Subjects for which this last assessment is the baseline assessment will be censored at time 0.

Measurement	Formula
	(Date and time of event or censoring - date and time of first dose of study drug)/3600, rounded to one decimal

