Time to return to pre-RSV disease level for heart rate (hours) [Time-to event]	
Idem as Time to return to pre-RSV disease level for respiratory rate (hours) but for heart rate.
 
Normalization of heart rate (HR) will be derived from the answer to the corresponding question in the questionnaire “is this Pulse value normal for this patient?”

Time to clinical stability (hours) [Time-to event]	
The time from first dose of study drug until the time at which the each of the following criteria are met (=event):
 
 • Normalization of Oxygen supplementation (as in parameter Time to end of Oxygen supplementation), • Normalization of feeding/hydration (as in parameter Time to end of supplemental feeding/hydration) , • Normalization of respiratory rate (as in parameter Time to return to pre-RSV disease level for respiratory rate), and • Normalization of heart rate (as in parameter Time to return to pre-RSV disease level for heart rate). 
In case any of the four components is censored, the time to clinical stability will also be censored at the first time-point of the censored component.
 
Subjects who complete or withdraw from the study prior to the event will be censored at the date of completion or withdrawal. If the time is not available they will be censored at 12:00. In case of death the subject will be censored at the maximum observed number of hours until the occurrence of the event or censoring for all subjects achieving the event or being censored because of study completion or withdrawal.
 
(maximum(Date and time of event criteria or censoring) - date and time of first dose of study drug)/3600, rounded to one decimal

Time to return to pre-RSV disease level for body temperature (hours), [Time-to event]	
The time from first dose of study drug until the time to return to pre-RSV disease level. The return to pre-RSV disease level occurs when the observed value of the parameter is within the normal range (=event).
 
If no deterioration from pre-RSV disease levels occurred, the

Measurement	Formula										

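### Respiratory-rate and heart-rate recovery is timed as exact although site assessments thin out after discharge; an interval-censored analysis should sit beside the Cox model

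*SAP*

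**What the plan says.** SAP 5.3.1.3 bases return to the pre-RSV respiratory rate (RR) on the investigator's rating: "The return to pre-RSV disease level occurs when the observed value of the parameter is indicated by the investigator as normal". In full, the event is a value "indicated by the investigator as normal, and no later observed values are indicated by the investigator as abnormal (=event". Heart rate (HR) follows the same rule. SAP 5.3.1 adds: "Note that for time-to event variables the actual date times will be used". Censoring is on the right only: "Subjects with an abnormal value at the last assessment will be censored at that time".

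Time to clinical stability, in the same section, is the latest of four components. Two are these RR and HR times. The other two are the recorded end times of oxygen supplementation and of supplemental feeding or hydration.

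SAP 5.3.2.3 analyses these endpoints with Kaplan-Meier curves, a Cox model, and logrank and Gehan-Wilcoxon tests. Protocol 11.3 also names Cox for clinical stability.

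In the Time and Events Schedules, vital signs are twice daily in hospital. A child may go home after the Day 2 procedures. From then on children are "required to return to the hospital for follow-up assessments as an outpatient on Day 7, Day 10, Day 14, and Day 28" (Protocol 9.1.4), with windows of +2 days, or ±2 days at Day 28.

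Three further passages matter:
- For virus clearance, SAP 5.3.1.1 also defines the time "at which the virus is undetectable, using interval censoring", and SAP 5.3.2.1 analyses it with an accelerated failure time (AFT) model.
- The caregiver diary in Protocol Attachment 5 asks for a temperature (item 16) and a 15-second breath count (item 17): "Questions 16-17 are to be completed on the day of hospital discharge and during the morning assessment only through follow-up Day 14".
- Temperature has its own rule. The event "occurs when the observed value of the parameter is within the normal range (=event", with no investigator rating and no condition on later values.

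**The concern.** A normal rating shows only that recovery came at some time after the last abnormal rating. In hospital that uncertainty is about half a day. After an early discharge it is several days, and the plan places the event at the far end of the interval. Nothing in the documents requires RR and HR to be rated normal before discharge, which is the investigator's judgement.

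Discharge is itself a secondary endpoint and may differ between arms, so the comparison can partly measure the visit calendar. If the arms differ in the share of children who leave while rated abnormal, the hazard ratio can move away from 1 with no difference in recovery. Even with equal shares, late dating can blur a real benefit and cost power. Clinical stability inherits the problem because it takes the latest component: one abnormal RR or HR rating at discharge moves the composite to Day 7 or later.

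**Working it through.** **Width of the gap.** The earliest discharge is on Day 2, and the next scheduled site assessment falls on Day 7 to Day 9. That is 7 − 2 = 5 days to 9 − 2 = 7 days, or 120 to 168 h. Against 12 h in hospital, the interval is 10 to 14 times as wide.

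**Comparison with virus clearance.** Swabs are daily through Day 6 wherever the child is, so the gap in the first week is about 24 h. The endpoint with the narrower gap has the interval-censored analysis, and the one with the wider, discharge-dependent gap does not.

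**Size.** The documents state no power, event count or effect for these endpoints, so there is no figure to reproduce. A simulation used 60 children per arm (SAP 1.2.1), assessments every 12 h plus one at discharge, then Days 7, 10 and 14 (each +0 to 48 h) and Day 28. True recovery and discharge times were correlated lognormals; their medians and correlation are assumptions. The event was the first normal value with no later abnormal one. Each scenario had 600 runs. A hazard ratio (HR in the table) below 1 means that the active arm appears slower. Paired entries are control / active.

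| True median recovery, h | Median discharge, h | Correlation | Left while abnormal | Apparent median, h | HR | False "slower" (nominal 2.5%) | Interval-censored AFT: time ratio; false "slower" |
|---|---|---|---|---|---|---|---|
| 60 / 60 | 84 / 63 | 0.8 | 17% / 42% | 69 / 98 | 0.75 | 32.7% | 1.04; 6.2% |
| 60 / 60 | 84 / 63 | 0.5 | 26% / 44% | 72 / 101 | 0.81 | 19.8% | 1.03; 3.5% |
| 36 / 36 | 84 / 63 | 0.5 | 6% / 14% | 42 / 42 | 0.86 | 9.8% | 1.01; 2.8% |
| 36 / 36 | 84 / 63 | 0.8 | 1% / 6% | 42 / 42 | 0.91 | 7.0% | 1.01; 3.2% |
| 36 / 36 | 120 / 90 | 0.9 | 0% / 0% | 42 / 42 | 0.98 | 3.0% | not run |
| 36 / 36, with 10% transient abnormal readings | 120 / 90 | 0.9 | 0% / 0% | 136 / 108 | 1.06 | 1.3% | not run |

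Monte Carlo error is about 1 to 4 percentage points on the rejection rates.

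**With a true benefit.** With recovery and discharge both 25% faster (correlation 0.5; 26% / 25% left while abnormal), the apparent medians were 71 h and 53 h and the hazard ratio was 1.31. The logrank test on assessment times found the benefit in 27% of runs. The interval-censored AFT found it in 71%, with a time ratio of 0.75.

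**A second set of assumptions** (300 runs per scenario; placebo median recovery 40 to 60 h; median discharge 100 h on placebo and 70 to 80 h on active; correlation 0.6; 3% to 36% leaving while abnormal) gave hazard ratios of 0.76 to 0.89 with no true effect. With recovery 20% faster the true hazard ratio was about 1.40, and the assessment-dated one was 1.21 to 1.30. On the log scale, ln 1.21 / ln 1.40 = 0.191 / 0.336 = 0.57 and ln 1.30 / ln 1.40 = 0.262 / 0.336 = 0.78, so 57% to 78% of the effect survives. Power was 18% to 28%, against 45% to 47% for the interval-censored AFT.

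**The case against.** A reader might infer that the arm that goes home earlier will look slower to recover. The documents do not support that as a general result. It needs more children in that arm to leave while rated abnormal, and the documents do not give that share. When almost none do, the hazard ratio is 0.98. Because RR and HR need sustained normality, inpatients have more readings that can reset the clock, which gave 1.06 in favour of the early-discharge arm.

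A reader might also infer that a real benefit could be reversed. In every simulated case with a true benefit the active arm still looked faster. The low hazard ratios require shorter stay with no effect on recovery, an unlikely pairing if discharge follows clinical status.

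Nor is it right that nothing is recorded before Day 7. Caregivers measure temperature and breaths each morning, and the temperature rule does not exclude their readings. The breath count, however, cannot answer whether the investigator rates the rate normal for that child, and no home heart rate is measured. The RR and HR gap therefore stands.

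Three limits also stand. The oxygen and feeding components use recorded end times. These are secondary endpoints, and the primary viral-load analysis is untouched. The AFT comparator was a lognormal model fitted to lognormal data, so its power advantage is flattered.

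**Conclusion.** The point holds for RR, HR and the RR and HR parts of clinical stability. Assessment times are used as exact, the assessment grid depends on discharge, and no planned analysis allows for it. Over the assumptions tried, and without transient abnormal readings, the hazard ratio with no true effect ran from about 0.75 to 0.98. False "slower" results occurred in 3% to 33% of runs against a nominal 2.5%. A true benefit was attenuated. Both size and direction turn on the share in each arm who leave while rated abnormal, which only the trial data can show. Temperature is affected only if caregiver readings are not used, which the SAP does not state.

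Interval censoring removes most of the bias but not all of it. The time ratio was 1.01 to 1.04, with false "slower" results in 2.8% to 6.2% of runs, because discharge is correlated with recovery. This is a worthwhile, inexpensive addition to secondary analyses and no threat to the primary conclusion.

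**What to change.** Before unblinding, amend SAP 5.3.1.3 and 5.3.2.3 as follows.

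- Keep the protocol-named Cox model. Beside it, prespecify an interval-censored analysis of RR and HR, using either proportional hazards or the AFT already planned for virus clearance. The interval runs from the last abnormal to the first sustained-normal assessment.
- For clinical stability, use the maximum of the component left limits and the maximum of the right limits. Oxygen and feeding end times stay exact, so each enters as both its left and its right limit. If the latest component is one of these, the composite remains exact.
- State how children assigned 0 hours enter the model, since a log-time AFT cannot take an exact zero. Left-censoring at the first post-dose assessment is one possibility.
- State whether caregiver temperatures count for the temperature endpoint. If they do, say which normal range applies: the SAP ranges depend on the measurement method, which diary item 16 does not ask for. Do not feed caregiver breath counts into the investigator-rated RR endpoint.
- Report by arm the number discharged with RR or HR still rated abnormal. This shows directly whether the conditions for bias arose.

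The interval-censored AFT could also serve as the sensitivity analysis that Protocol 11.3 leaves to the SAP if proportional hazards fails; at present the SAP offers a log-log plot and rank tests on the same times. The cost is extra programming and one more secondary analysis to report. No new data are needed.

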	
time will be set to time of first dose of study drug and the value will be set to 0 hours.
 
Subjects with an abnormal value at the last assessment will be censored at that time. Subjects for which this last assessment is the baseline assessment will be censored at time 0.
 
(Date and time of event or censoring - date and time of first dose of study drug)/3600, rounded to one decimal.
 
The normal ranges can be found in the table below:
 
  
 Measurement method	Normal temperature range	
   
 Rectal	36.6°C to 38°C (97.9°F to 100.4°F)	
 
 Ear	35.8°C to 38°C (96.4°F to 100.4°F)	
 
 Oral	35.5°C to 37.5°C (95.9°F to 99.5°F)	
 
 Axillary	34.7°C to 37.3°C (94.5°F to 99.1°F)	
  
	Measurement method	Normal temperature range	Rectal	36.6°C to 38°C (97.9°F to 100.4°F)	Ear	35.8°C to 38°C (96.4°F to 100.4°F)	Oral	35.5°C to 37.5°C (95.9°F to 99.5°F)	Axillary	34.7°C to 37.3°C (94.5°F to 99.1°F)
Measurement method	Normal temperature range										
Rectal	36.6°C to 38°C (97.9°F to 100.4°F)										
Ear	35.8°C to 38°C (96.4°F to 100.4°F)										
Oral	35.5°C to 37.5°C (95.9°F to 99.5°F)										
Axillary	34.7°C to 37.3°C (94.5°F to 99.1°F)										
Time to SpO ₂ ≥ 93% on room air (hours) [Time-to event]	
The time from first dose of study drug until the time of first SpO₂ measurement ≥ 93% on room air, and where no supplemental oxygen supplementation is given at or after this time point and where no value < 93% are measured after this time point.
 
Subjects with SpO₂<93% on room air or who are still on oxygen supplementation at the last SpO₂ assessment will be censored at the date and time of the last SpO₂ assessment.
 
If no oxygen supplementation was necessary post-baseline and the subject had SpO₂ measurement ≥ 93% on room air at baseline and all post baseline measurements, the value will be set to 0.
 
(Date and time of event or censoring - date and time of first dose of study drug)/3600, rounded to one decimal
										
Incidence of acute otitis media	Did the subject have acute otitis media after first dose of study drug (use high-level term “Middle ear infections and										

Measurement	Formula

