5.3.2.3. RSV clinical outcome

Length of hospital stay and time to readiness for discharge.

These time-to event variables will be analyzed as indicated above using Kaplan-Meier analysis, and will also be compared between each active treatment group and placebo using an accelerated failure time (AFT) model. .

Additionally, the time-to event data will be analyzed using the logrank test and Gehan-Wilcoxon method comparing each active treatment to placebo

Duration of intensive care unit (ICU) stay (hours) [Duration]

The duration in the ICU will be analyzed descriptively for all subjects and by subgroup of subjects staying / not staying in the ICU at the time of first dose of study drug.

Requirement for intensive care or supplemental support

The requirement for intensive care unit (ICU) stay, for oxygen supplementation, for noninvasive mechanical ventilation support, for invasive mechanical ventilation support, for supplemental feeding/hydration will be analyzed similarly. These requirement parameters will only be calculated for those subjects that don't require intensive care or supplemental support (depending on the parameter of interest) before first dose of study drug.

The proportion of subjects within the requirement categories (yes and no) will be shown in a frequency tabulation (with corresponding 95% CI) and per treatment group.

In addition, a stratified logistic regression model will be used to analyze the outcome

The analyses of the requirement parameters will answer the question:

Is there a treatment difference in preventing the use of intensive care or supplemental support?

Time to end of intensive care or supplemental support

These time-to event parameters will be analyzed for those subjects that require intensive care or supplemental support (depending on the parameter of interest) before first dose of study drug,

Kaplan-Meier analysis and stratified Gehan test to compare active treatment groups versus placebo will be used.

These time-to event parameters will answer the question:

Is there a treatment difference in the time to no longer requiring intensive care or supplemental support?

While we cannot integrate the results on the requirement for intensive care or supplemental support and the time to end of intensive care or supplemental support they are conceptually linked. We will combine the p-values for both independent tests for the comparison of each active group versus placebo using the method of Liptak^[3].

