Additionally these time-to event parameters will be analyzed for all ITT-i subjects using Kaplan-Meier analysis as indicated above and using a stratified Gehan test to compare between treatment groups

Time to clinical stability and Time to return to pre-RSV disease level

These time-to event parameters will be analyzed as indicated above using Kaplan-Meier analysis.

The differences in time of active dose regimens versus placebo treatment will be estimated using a Cox proportional hazard model; as baseline covariates, stratification factors, absence/presence of other viral or bacterial infections, and baseline log₁₀ viral load will be added. Treatment effect versus placebo will be reported, including 95% confidence intervals. A Log-log plot of survival will be added to check the proportional hazard assumption.

Additionally, the time-to event data will be analyzed using the logrank test and Gehan-Wilcoxon method.

Incidence of acute otitis media and all-cause mortality

The incidence of acute otitis media and of all-cause mortality will be analyzed similarly. Note that these incidences are only analyzed if any subjects have acute otitis media or if any deaths occur.

The proportion of subjects with presence/absence of acute otitis media and who died yes/no will be shown in a frequency tabulation (with corresponding 95% CI) and per treatment group.

A stratified logistic regression model will be used to analyze the outcome.

Relationship between RSV RNA viral load and clinical outcome

The following relationships will be investigated:

RSV RNA log₁₀ viral load AUC_{0-144h} versus

- Requirement for oxygen supplementation
- Time to end of Oxygen supplementation

- Length of hospital stay
- Time to readiness for discharge
- Length of hospital stay since hospital admission
- Time to readiness for discharge since hospital admission
- Time to clinical stability
- Time to return to pre-RSV functional status

The definitions of these parameters can be found in sections [5.3.1](#).

A Tabulation of the requirement for oxygen supplementation will be presented by quartiles of viral load AUC_{0-144h} .

Kaplan-Meier analysis by quartiles of viral load AUC_{0-144h} will be done for the time to variables.

Relationship between RSV RNA viral load and signs and symptoms of RSV infection

The following relationships will be investigated:

Quartiles of viral load AUC_{0-144h} versus

- Severity of signs and symptoms of RSV infection as rated by the clinician.

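### The vital-sign recovery endpoints count children with no deterioration as events at 0 hours in all-ITT-i tests, which pulls the recovery hazard ratio towards 1 when such events are balanced between arms

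*SAP*

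**What the plan says.** SAP 5.3.1.3 defines the times to return to pre-RSV level.

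- **Respiratory rate.** The event is a value "indicated by the investigator as normal, and no later observed values are indicated by the investigator as abnormal (=event". The 0-hour rule reads: "If no deterioration from pre-RSV disease levels occurred, the time will be set to time of first dose of study drug", and the value is then 0 hours.
- **Heart rate.** "Idem as Time to return to pre-RSV disease level for respiratory rate (hours) but for heart rate".
- **Body temperature.** "The return to pre-RSV disease level occurs when the observed value of the parameter is within the normal range (=event". The same 0-hour rule follows, but without the requirement that no later value be abnormal.
- **Clinical stability.** This is the latest of four components (oxygen, feeding, respiratory rate, heart rate), so it is 0 hours only when all four are.

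SAP 5 places all efficacy analyses on the ITT-i set. For clinical stability and return to pre-RSV level, SAP 5.3.2.3 says: "The differences in time of active dose regimens versus placebo treatment will be estimated using a Cox proportional hazard model". The covariates are the stratification factors, co-infection and baseline viral load. Logrank and Gehan-Wilcoxon tests are added. Neither this list nor the candidate covariates in SAP 5.3.2 include vital-sign status at first dose.

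The support endpoints (ICU, oxygen, ventilation, feeding) also set the time to 0 when no support was needed, but SAP 5.3.2.3 handles that: "These time-to event parameters will be analyzed for those subjects that require intensive care or supplemental support" before first dose. Children not needing support before first dose are covered by a yes/no requirement analysis. The two p-values are combined by Liptak's method, and an all-ITT-i analysis is additional.

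**The concern.** The question is whether lumicitabine speeds the return of vital signs to normal. A child who never left normal has nothing to return from. Counting that child as recovered at 0 hours puts a block of tied events at the start of follow-up. When the block is balanced between arms, it says the hazards are equal, whatever happens later among children who were abnormal.

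The Cox estimate then averages a ratio near 1 at time 0 with the recovery effect afterwards. Gehan-Wilcoxon suffers most because it weights by the number at risk, which is largest at time 0. A real recovery effect could be reported as smaller than it is, with a lower chance of being detected. The SAP avoids this for the support endpoints and gives no reason for treating the vital signs differently.

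**Working it through.** **1. Are the 0-hour children events?** Yes, by the definition. A child normal at every assessment meets the respiratory-rate event definition, and the separate rule censoring at time 0 covers a different child, whose last assessment is baseline and abnormal. The SAP does not put the word event beside the 0-hour value and does not state how ties are handled.

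**2. Is there a plan figure to reproduce?** No. The plan gives no power, hazard ratio or event count for these endpoints. Its 97% power concerns the viral-load primary endpoint.

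**3. Inputs.** From the documents: 60 children per regimen, 1:1:1 allocation, 28 days of follow-up, 95% intervals (so nominal two-sided 5%). Assumed: placebo median recovery 72 h, exponential times, true recovery hazard ratio 1.5 or 1.8 among children abnormal at first dose, and a share p of 0-hour events from 10% to 50%, equal in both arms.

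**4. Algebra.** Let n be the number of children in the two arms together. The block at time 0 adds variance but no expected signal.

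- Logrank: the later events contribute variance n(1−p)/4 and the block n·p(1−p)/4, so Z is multiplied by √[1/(1+p)].
- Gehan: squared at-risk weights give later variance n³(1−p)³/12 and block variance n³p(1−p)/4, so Z is multiplied by √{[(1−p)²/3] / [(1−p)²/3 + p]}.

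At p = 30% these are √(1/1.3) = 0.877 and √(0.1633/0.4633) = 0.594. At p = 50% they are 0.816 and 0.378.

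**5. Simulation** (60 against 60, 1,500 runs). Power is shown as all ITT-i → restricted to children abnormal at first dose.

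| True HR | p | All-ITT-i Cox HR | Cox power | Logrank power | Gehan power |
|---|---|---|---|---|---|
| 1.5 | 10% | 1.44 | 48.9 → 53.2% | 49.5 → 53.9% | 32.3 → 43.7% |
| 1.5 | 20% | 1.38 | 39.7 → 48.0% | 41.5 → 48.5% | 23.7 → 39.5% |
| 1.5 | 30% | 1.32 | 31.3 → 43.9% | 34.9 → 44.4% | 16.0 → 35.4% |
| 1.5 | 40% | 1.27 | 24.7 → 38.8% | 29.1 → 39.8% | 11.5 → 31.5% |
| 1.5 | 50% | 1.22 | 17.0 → 31.0% | 22.3 → 31.5% | 7.8 → 25.4% |
| 1.8 | 30% | 1.51 | 58.5 → 73.9% | 63.3 → 74.5% | 27.5 → 63.1% |

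The restricted analysis returns a hazard ratio of 1.50 to 1.52 (true 1.5) and 1.83 (true 1.8, p = 30%). Efron and Breslow ties agree to within 0.01 here. On a 12-hour assessment grid at p = 30%, a true 1.8 becomes 1.48 (Efron) or 1.44 (Breslow).

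**6. Cross-checks.**

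- Logrank, HR 1.8, p = 30%: restricted power 74.5% means an expected Z of 1.96 + 0.659 = 2.619. Then 2.619 × 0.877 = 2.297, and Φ(2.297 − 1.96) = 63.2%, against 63.3% simulated.
- Gehan, same setting: (1.96 + 0.3345) × 0.594 = 1.363, and Φ(1.363 − 1.96) = 27.5%, as simulated.
- Schoenfeld, restricted, HR 1.5, p = 30%: 120 × 0.7 = 84 events, √(84/4) × ln 1.5 = 1.858, and Φ(1.858 − 1.96) = 45.9%, against 44.4% simulated.
- Under the null at p = 30%, rejection rates are 5.0% (Cox), 5.2% (logrank) and 4.4% (Gehan).

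**7. If the drug also changes later deterioration.** For respiratory and heart rate, 0 hours requires staying normal, so the shares can differ by arm.

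- Mild: 30% normal at first dose, of whom 20% (placebo) and 13.3% (active) later worsen. Zeros are 30% × 0.80 = 24% and 30% × 0.867 = 26%. A true 1.5 gives 1.38; Cox power is 41% against 47% restricted, Gehan 24% against 40%.
- Extreme: 40% normal, of whom 30% and 10% later worsen. Zeros are 28% and 36%. A true 1.5 gives 1.45; Cox power is 50% against 45% restricted, logrank 52% against 45%.
- A separate simulation (500 runs, 12-hour grid) took 40% normal at first dose and a hazard ratio of 1.5 for both recovery and prevention. With half of the initially normal placebo children later deteriorating, Cox gave 1.45 with 50% power on all ITT-i, against 1.46 with 34% restricted. With none deteriorating it gave 1.25 with 21%, against 1.50 with 35%.

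**The case against.** The strongest reply is that 0 hours is not a pure baseline state. For respiratory and heart rate, one later abnormal reading moves the child to a later event time, and readings continue twice daily in hospital and at visits to Day 28. A reader might infer that the 0-hour events are settled before the drug can act. The definition does not support that: staying normal is partly a post-dose outcome. The all-ITT-i analysis can therefore pick up a preventive effect that a bare restriction discards, and step 7 shows this can outweigh the power lost. This part stands. It rules out an unconditional claim of lost power and makes outright replacement of the planned analysis a trade-off.

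A reader might also infer that most children have a normal temperature at first dose. The documents give no such share for any parameter. For clinical stability a large 0-hour share should not be assumed either, because all four components must be 0 in children hospitalised, or in the emergency room, with acute respiratory illness.

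These are secondary phase 2 endpoints with no stated power, and attenuation is conservative. That limits the importance of the point. It does not make the hazard ratio interpretable as a recovery effect.

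**Conclusion.** The point holds conditionally. Where 0-hour events are similarly frequent in both arms, the all-ITT-i Cox estimate understates the recovery hazard ratio: a true 1.5 becomes about 1.38 at 20% zeros and 1.27 at 40%. All three tests then lose power, Gehan-Wilcoxon most. The direction is firm under that condition; the size depends on assumed shares, a 72 h median and exponential recovery.

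The powers use 60 per arm. SAP 5.1.1 expects 120 ITT-i children in all, or 120/3 = 40 per arm, where both sets of powers would be lower; the Z factors in step 4 do not depend on the number of children.

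Type I error and the primary endpoint are not affected. For Cox and logrank the power loss may vanish or reverse if the drug prevents later deterioration. The missing element is an analysis that separates recovery from prevention, which the SAP already has for support endpoints.

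**What to change.** In SAP 5.3.2.3, treat each vital-sign endpoint as the support endpoints are treated:

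1. Run Cox, logrank and Gehan-Wilcoxon in children whose parameter is abnormal at the last pre-dose assessment; for clinical stability, in children not stable at first dose. Status is fixed before dosing, so the comparison remains a randomised one.
2. In children normal (or stable) at first dose, analyse later abnormality as yes/no.
3. Combine the two p-values by Liptak's method, so that any preventive effect is kept. The two groups do not overlap, so the tests are independent.
4. Report the share of 0-hour children by arm.
5. Keep the all-ITT-i analysis alongside.

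The SAP should also state that a 0-hour value is an event and how ties are handled. The cost is one baseline flag, some SAP text and slightly more analysis, with no new data. The downside is a smaller set for the restricted test.
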